7.1 Sample Size

The primary efficacy endpoint is the change from baseline at Day 42 in AISRS total score. The trial will compare the placebo arm to the centanafadine dose arms, randomized at a ratio of 1:1:1, with an overall alpha of 0.05 for the primary endpoint.

Based on the results at various dose strengths from phase 2 centanafadine trials, it is reasonable to expect a treatment difference of 5 points with a standard deviation (SD) of 12.5 in the mean change from baseline to Day 42 on AISRS total score in either the 200 mg TDD or 400 mg TDD arms. The planned sample size of 405 evaluable subjects (135 in each treatment arm) will yield at least 90% power to detect the treatment effects at a 2-tailed significance level of 0.05. The 2-sided alpha level for the final analysis is 0.05.

A sufficient number of subjects will be enrolled and randomized to achieve approximately 405 evaluable subjects in the double-blind treatment period (ie, subjects with an AISRS total score at baseline and at least 1 subsequent AISRS total score in the

Protocol 405-201-00014

double-blind treatment period). After allowance of 10% nonevaluable subjects in the double-blind treatment period, the total number of subjects to be randomized is 450 subjects (150 subjects in each treatment arm). In order to ensure 405 evaluable subjects, the number of nonevaluable subjects will be monitored in a blinded manner on an ongoing basis during the trial. The power and sample size were obtained using the PASS 14 (2015) statistical computing software.

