7.3.2 Secondary Efficacy Endpoint Analyses

7.3.2.1 Key Secondary Efficacy Endpoint Analysis

The key secondary efficacy endpoint is the change from baseline to Day 42 between treatment groups using the CGI-S. The estimand for the key secondary efficacy analysis is also the difference in outcome improvement if all subjects tolerated and adhered to their treatment. This approach is Estimand #3 recommended by the 2010 National Academy of Sciences' National Research Council report on prevention and treatment of missing data and ICH E9 (R1) Addendum. This key secondary efficacy endpoint will be analyzed by fitting the same MMRM model described in the primary analysis.

To control the overall experiment-wise type I error at 0.05 level, a fixed-sequence testing approach will be applied.

The statistical test will be performed in the following order:

- 1) Change from baseline to Day 42 in the double-blind treatment period in AISRS total score between centanafadine 400 mg TDD and placebo;
- 2) Change from baseline to Day 42 in CGI-S score between centanafadine 400 mg TDD and placebo;
- 3) Change from baseline to Day 42 in the double-blind treatment period in AISRS total score between centanafadine 200 mg TDD and placebo;
- 4) Change from baseline to Day 42 in CGI-S score between centanafadine 200 mg TDD and placebo.

Protocol 405-201-00014

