8.2 Key Secondary Efficacy Endpoint

The key secondary efficacy endpoint is the change from baseline of the double-blind treatment period to Day 42 using the CGI-S. This key secondary efficacy endpoint will be analyzed by fitting the same MMRM model described in the primary analysis.

To control the overall experiment-wise type I error at 0.05 level, A fixed sequence testing approach will be applied. The statistical test will be performed in the following order:

- 1) Change from baseline to Day 42 in the double-blind treatment period in AISRS total score between centanafadine 400 mg TDD and placebo;
- 2) Change from baseline to Day 42 in the double-blind treatment period in AISRS total score between centanafadine 200 mg TDD and placebo;
- 3) Change from baseline to Day 42 in CGI-S score between centanafadine 400 mg TDD and placebo;
- 4) Change from baseline to Day 42 in CGI-S score between centanafadine 200 mg TDD and placebo.

The testing procedure will stop at the first comparison where the p-value is ≥ 0.05 . None of the subsequent comparisons will be performed.

SAP 405-201-00014

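### The stated 90% power is a single-comparison figure: it fits 400 mg, but under the fixed sequence 200 mg has about 84% power in the SAP order and less in the protocol order

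*Protocol*

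**What the plan says.** Protocol 7.1 and the synopsis (Statistical Methods) plan on the basis that "it is reasonable to expect a treatment difference of 5 points with a standard deviation (SD) of 12.5" for the Day 42 AISRS change, and apply this "in either the 200 mg TDD or 400 mg TDD arms". The next sentence gives 405 evaluable subjects, 135 per arm, and claims that this number "will yield at least 90% power to detect the treatment effects at a 2-tailed significance level of 0.05". SAP 4 repeats the power sentence with the same numbers, but its effect-size sentence names no arm. None of the three places calls the figure per-comparison power or refers to the order of testing.

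The tests are ordered. Protocol 7.3.2.1 states: "To control the overall experiment-wise type I error at 0.05 level, a fixed-sequence testing approach will be applied". SAP 8.2 spells out the consequence: "The testing procedure will stop at the first comparison where the p-value is" 0.05 or more, and nothing later is then tested. The two documents list different sequences:

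| Step | Protocol 7.3.2.1 | SAP 8.2 |
|---|---|---|
| 1 | AISRS, 400 mg | AISRS, 400 mg |
| 2 | CGI-S, 400 mg | AISRS, 200 mg |
| 3 | AISRS, 200 mg | CGI-S, 400 mg |
| 4 | CGI-S, 200 mg | CGI-S, 200 mg |

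The synopsis and Protocol 7.3.1 also place 400 mg ahead of 200 mg for AISRS. No CGI-S effect size, SD or correlation with AISRS is given for planning.

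**The concern.** The power sentence speaks of treatment effects in the plural and follows directly on an effect assumed for either dose. A reader will take it that each dose has at least a 90% chance of confirmatory success if the assumptions hold. For 200 mg that cannot be so: a significant 200 mg result counts only in trials where 400 mg has already succeeded, and in the protocol order only where 400 mg CGI-S has succeeded as well. Fixed-sequence testing keeps the full 0.05 for each test, and the price is power for the later tests. What is at stake is a correct account of the risk of failing to confirm one of the two doses. Validity is not in question.

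**Working it through.** **Inputs.** From Protocol 7.1: difference 5, SD 12.5, 135 evaluable per arm, allocation 1:1:1, two-sided 0.05. From Protocol 7.3.2.1 and SAP 8.2: the test orders. All 135 per arm are taken as fully observed at Day 42, so any loss from missing data is a separate matter.

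**1. Reproduce the plan's figure.** The expected test statistic for one dose against placebo is

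5 / (12.5 × √(2/135)) = 0.4 × √67.5 = 3.286.

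Normal approximation: Φ(3.286 − 1.960) = Φ(1.326) = 90.8%. Noncentral t with 268 degrees of freedom: 90.6%. The smallest size giving 90% by the normal formula is 132 per arm, and 405/0.9 = 450 randomized. The plan's figure therefore reproduces as a single comparison.

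**2. Correlation of the two dose statistics.** Both use the same placebo mean. With equal arms of size n, the covariance of the two differences is σ²/n and each variance is 2σ²/n, so the correlation is (σ²/n)/(2σ²/n) = 0.5.

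**3. Power for 200 mg in the SAP order.** The dose is declared effective on AISRS only if both statistics exceed 1.960:

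P(Z400 > 1.960 and Z200 > 1.960), means 3.286, correlation 0.5 = 84.4%.

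Simulating 400,000 trials with t-tests gave 84.3% with a pooled variance and 84.2% with pairwise variances.

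**4. Where the loss arises.** Of the 15.6% of trials that fail to declare 200 mg, 100 − 90.8 = 9.2 points come from its own test. The other 90.8 − 84.4 = 6.4 points are trials in which 200 mg would be nominally significant but 400 mg failed first.

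**5. Sensitivity to the correlation.**

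| Correlation | Power for 200 mg, SAP order |
|---|---|
| 0 | 82.4% |
| 0.5 (this design) | 84.4% |
| 1 | 90.8% |

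The single-comparison figure is recovered in full only if the two statistics are perfectly correlated.

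**6. Size that 90% would need.** In the SAP order, about 157 evaluable per arm, against 135 planned. This is given for scale only.

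**7. Protocol order.** Requiring 400 mg CGI-S to succeed as well can only remove trials from the event in step 3, so the power is below 84.4%. The size of the reduction depends on the CGI-S effect and its correlation with AISRS, neither of which is given.

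**The case against.** The strongest reply is that nothing has been miscalculated. The figure is stated "at a 2-tailed significance level of 0.05", which reads naturally as one comparison, and quoting pairwise power for a multi-dose trial is common. Taken alone, the 200 mg comparison does have about 91% power, and once reached it has 0.844/0.908 = 93%. The 84% is a different quantity, the chance that both doses win. This stands as far as it goes: the sponsor's arithmetic is right, and what is missing is the label and the second figure. It does not make the unlabelled sentence correct for a dose that the plan never tests on its own.

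Three stronger readings are tempting, and the documents do not support them.

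- A reader might infer that 90% power to confirm both doses was promised because 200 mg carries half of the primary objective. Protocol 2.3 joins the doses with *or*, Protocol 2.2 describes the 200 mg arm as exploring a minimum effective dose, and one sentence of SAP 8.1.1 frames the primary analysis around 400 mg alone, although the same section also names both doses.
- A reader might put a number on the protocol order. With an assumed CGI-S effect of 0.30 to 0.40 SD and an assumed AISRS/CGI-S correlation of 0.5 to 0.9, the result runs from about 62% to 82%. That spread comes mainly from the assumed CGI-S effect, so no figure is claimed here.
- A reader might extend the criticism to the chance of winning all four tests. Protocol 7.1 makes no power claim for CGI-S.

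It can also be said that the ordering did not matter in the event. The outputs filed with the SAP give Day 42 p-values of 0.0009 (400 mg) and 0.0021 (200 mg) for AISRS, and 0.0245 and 0.0073 for CGI-S, so either sequence runs to the end. That is true of the result. It does not change the power that the design had.

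**Conclusion.** The point holds as a misstatement of design power, not as an error of arithmetic. The stated figure is the marginal power of one comparison and is correct for 400 mg against placebo on AISRS. For 200 mg on AISRS, the power under the fixed sequence is about 84% in the SAP order, some 6 percentage points below the single-comparison figure, and the chance of missing a true effect is about 16%, where the text implies 10% or less. This rests on both true differences being 5, SD 12.5, 135 per arm fully observed, and the 0.5 correlation that follows from 1:1:1 allocation with a shared placebo arm. In the protocol order the power is certainly lower, but the documents do not allow the amount to be calculated. Control of type I error is not affected.

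**What to change.** Restate the power sentence in Protocol 7.1, the synopsis and SAP 4 along these lines: *about 90% power for 400 mg versus placebo on AISRS (per comparison); about 84% for 200 mg versus placebo on AISRS under the fixed sequence in the SAP order, with both true differences 5, SD 12.5 and 135 per arm.*

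Reconcile the test orders in Protocol 7.3.2.1 and SAP 8.2, so that the 200 mg figure belongs to the order retained. If the protocol order is kept, state the CGI-S effect and the AISRS/CGI-S correlation assumed, and report the power that follows from them.

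The cost is a few lines of text and a less favourable stated figure for 200 mg. The sample size, tests and alpha do not change.

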7.1.1 Datasets for Analysis

The following samples are defined for this trial:

- **Enrolled Sample:** comprises all subjects who signed an eICF for the trial and enrolled into the single-blind placebo run-in period
- **Randomized Sample:** comprises of all subjects who were randomized in the double-blind treatment period. Subjects are considered randomized when they are assigned a treatment group by eCRF at the end of the single-blind placebo run-in period. A subject receiving IMP outside of the eCRF will not be considered randomized, but safety will be reported.
- **Safety Sample:** comprises those randomized subjects in the double-blind treatment period who receive at least 1 dose of double-blind IMP as indicated on the dosing record. Subjects will only be excluded from this population if there is documented evidence (ie, drug dispensed = drug returned or no IMP dispensed) that the subject did not take IMP. If a subject is dispensed IMP and is lost to follow-up, he/she will be considered exposed.
- **Efficacy Sample:** the Full Analysis Set (FAS) comprises all subjects in the Safety Sample who have a baseline value and at least 1 valid post-randomization efficacy evaluation for AISRS total score in the double-blind treatment period.

The core dataset for all efficacy analyses is the FAS, which is created based on the intent-to-treat (ITT) principle. However, as will be described below, in order to handle missing data and restrictions imposed by different types of analyses (eg, change from baseline analysis), datasets derived from the FAS dataset will be used for the efficacy analysis.

7.2 Handling of Missing Data

The AISRS is utilized as the primary efficacy assessment of a subject's level of ADHD symptoms. This 18-item scale directly corresponds to the 18 DSM-5 symptoms of ADHD where 9 Inattentiveness items alternate with 9 Hyperactivity/Impulsivity items. Each item is scored as follows: 0 (none), 1 (mild), 2 (moderate), 3 (severe). For all items, 0 is the "best" rating and 3 is the "worst" rating. The maximum total score for the scale is 54 points, with 27 points for each subscale. The AISRS total score is the sum of the Inattentiveness and Hyperactivity/Impulsivity subscale scores. The range of the AISRS

Protocol 405-201-00014

total score is from 0 to 54. The AISRS Inattentive subscale score and Hyperactivity/Impulsivity subscale score, as well as the AISRS total score is set to be missing if more than one item of a subscale is missing for Inattentiveness subscale or Hyperactivity/Impulsivity subscale, separately. If one item is missing for a given subscale (Inattentiveness or Hyperactivity/Impulsivity), then the subscale score will be derived as the mean of scores for non-missing items multiplied by 9. All imputed scores are rounded to the first decimal place.

The mixed-effect model repeated measures (MMRM) assumes data are missing at random (MAR), which is a reasonable assumption in longitudinal clinical trials in ADHD. However, the possibility of “missing not at random” (MNAR) data can never be ruled out. As sensitivity analyses, either selection model⁴¹ pattern-mixture model^{42,43,44,45} or shared parameter model⁴⁶ will be used to explore data missing mechanisms of MNAR and investigate the response profile of dropout reason. Pattern Mixture Models based on Multiple Imputation (MI) with mixed missing data mechanisms will be used to investigate the response profile of dropout subjects by last dropout reason under MNAR mechanism for the following 3 scenarios: 1) Dropout reasons due to either AE or lack of efficacy as MNAR, 2) Dropout reasons due to either AE or lack of efficacy or subject withdrew consent as MNAR, 3) All dropouts as MNAR using both 1) Delta adjustment imputation method which is to departure from MAR assumption by progressively increasing the delta until conclusion from the primary analysis is overturned, and 2) Placebo based imputation methods in which missing data for both placebo and drug group are imputed based on the imputation model derived from placebo data. If drug improved outcomes prior to dropout, this benefit is carried into subsequent imputed values, but will diminish over time in accordance with the correlation structure. Details of these exploratory analyses will be provided in the statistical analysis plan (SAP).

7.3 Primary, Secondary, and Exploratory Endpoint Analyses

7.3.1 Primary Efficacy Endpoint Analysis

The objective of the primary efficacy analysis is to compare the efficacy between centanafadine (SR 200 mg TDD or SR 400 mg TDD) and placebo. The primary efficacy endpoint is the change from baseline to Day 42 in AISRS total score. For analysis of the double-blind treatment period data, baseline is defined as the last available measurement prior to the first dose of double-blind IMP in the double-blind treatment period.

The estimand for the primary efficacy analysis is the difference in outcome improvement if all subjects tolerated and adhered to their treatment. This approach is Estimand #3,

Protocol 405-201-00014

recommended by the 2010 National Academy of Sciences' National Research Council report on prevention and treatment of missing data and ICH E9 (R1) "Addendum to Statistical Principles for Clinical Trials on Choosing Appropriate Estimands and Defining Sensitivity Analyses in Clinical Trials".

This estimand focuses on the efficacy of centanafadine (SR 200 mg TDD or SR 400 mg TDD) in change from the baseline in AISRS total score. The objective of this trial is consistent with the election of an efficacy rather than effectiveness estimand.

The primary analysis will be performed on the Efficacy Sample which includes all randomized subjects who took at least 1 dose of IMP in the double-blind treatment period and who have both baseline and at least 1 post-randomization AISRS total score during the double-blind treatment period. The primary efficacy analysis will be performed by fitting a MMRM analysis with an unstructured variance covariance structure in which the change from baseline in AISRS total score at the scheduled double-blind treatment period visits will be the dependent variable based on the observed cases (OC) data set. The model will include fixed class effect terms for treatment, trial center, visit day, and an interaction term of treatment by visit day. The model will also include baseline values for the double-blind treatment period of AISRS total score and the interaction term of baseline values of AISRS total score by visit day as covariates. The primary comparison between the centanafadine (400 mg TDD group or 200 mg TDD group) and the placebo group at Day 42 in the double-blind treatment phase will be estimated as the difference between Least Squares means utilizing the computing software SAS procedure PROC MIXED. The comparison between the centanafadine (400 mg TDD group or the 200 mg TDD group) and the placebo group will be tested at a significance level of 0.05 (2-sided) in the order of 1) 400 mg versus placebo, and 2) 200 mg versus placebo. If there is a convergence problem with the unstructured variance covariance matrix of the MMRM model, the following structures other than unstructured will be used in order of 1) heterogeneous toeplitz, 2) heterogeneous autoregressive of order 1, and 3) heterogeneous compound symmetry and the first (co)variance structure converging to the best fit will be used as the primary analysis. If a structured covariance has to be used, the "sandwich" estimator of the standard error of the fixed effects parameters will be used in order to deal with possible model misspecification of the covariance matrix. Details of this analysis will be provided in the SAP.

Small centers will be defined as centers that do not have at least 1 evaluable subject (evaluable with regard to the primary efficacy variable) in each treatment arm in the double-blind treatment period. All small centers will be pooled to form "pseudo centers" for the purpose of analysis according to the following algorithm. Small centers will be

Protocol 405-201-00014

ordered from the largest to the smallest based on the number of evaluable subjects (ie, subjects who have baseline and at least 1 post-baseline value for the primary endpoint in the double-blind treatment period). The process will start by pooling the largest of the small centers with the smallest of the small centers until a non-small center is formed. This process will be repeated using the centers left out of the previous pass. In case of ties in center size, the center with the smallest center code will be selected. If any centers are left out at the end of this process, they will be pooled with the smallest pseudo centers, or if no pseudo centers exist, they will be pooled with the smallest non-small center.

In the case of gross violations of the linear model assumptions, nonparametric van Elteren test will be performed to compare the treatment effect at Day 42 in the double-blind treatment period on both last-observation-carried-forward (LOCF) and MI data. Details will be provided in the SAP.

7.3.1.1 Sensitivity Analyses

7.3.1.1.1 Sensitivity Analyses for Missing at Random Assumption

Traditionally the dropout mechanisms are divided into 3 types⁴³: (1) missing completely at random (MCAR), in which the probability of dropout doesn't depend on the observed data and the missing data; (2) MAR, in which the probability of dropout depends on the observed data, and (3) MNAR, where the probability of dropout depends on the missing data and possibly the observed data.

Most of MNAR methods⁴¹ have treated all observations with dropout as if they fall within the same dropout type. In practice, we would find that different dropout reasons may be related to the outcomes in different ways, for example, detailed dropout reasons for this trial are: AE, lack of efficacy, death, reasons unrelated to medical condition, withdrawal of informed consent, lost to follow-up, rash, pregnancy, and termination of all or part of the trial by sponsor. Dropout due to an AE, rash, and LOE may lead to MNAR dropout. Subjects that withdrew consent may also lead to MNAR dropout. However, it is debatable whether a dropout caused by subjects that withdrew consent are MAR or MNAR. Except AE, rash, LOE, and subjects that withdrew consent, all the other dropout reasons may be assumed as either MCAR or MAR dropout.

As sensitivity analyses for MAR assumptions, analyses for MNAR will be carried out. Pattern Mixture Models based on MI with mixed missing data mechanisms will be used to investigate the response profile of dropout subjects by last dropout reason under the MNAR mechanism for the following 3 scenarios:

- 1) Dropout reasons due to either AE, rash, or LOE as MNAR

Protocol 405-201-00014

- 2) Dropout reasons due to either AE, rash, or LOE or subject withdrew consent as MNAR
- 3) All dropouts as MNAR

Delta Adjustment Imputation Methods

This MNAR sensitivity analysis will be performed to address a departure from the MAR assumptions by progressively increasing the delta until the conclusion from the primary analysis is overturned. The delta is 0%, 10%, 20%, 30%, ..., 100% of the expected treatment difference of 5 points and/or the observed treatment difference between centanafadine and placebo from the primary analysis of MMRM model until the conclusion of the primary analysis is overturned. When delta=0 it is MAR. When delta > 0 it is MNAR.

- 1) Using Monte Carlo Markov Chain methodology from PROC MI to impute the intermittent missing data to a monotone missing pattern;
- 2) Using a standard MAR-based multiple imputation approach from PROC MI to impute the monotone missingness data
- 3) For subjects in the treated group and with a dropout reason of AE or LOE or subject withdrew consent, a delta will be added for all the values after the dropout time.
- 4) Using MMRM model in the primary analysis to analyzed the completed data using PROC MIXED on the multiple imputed data
- 5) Obtaining the overall results using PROC MIANALYZE

Placebo Based Imputation Methods

The placebo-based imputation methods will be similar to the “Standard” multiple imputations method, except the parameters for the imputation model will only be obtained from the placebo (control) group. Missing data for both the placebo and drug groups are imputed based on the imputation model derived from placebo data. If drug improved the outcomes prior to dropout, this benefit is carried into subsequent imputed values, but will diminish over time in accordance with the correlation structure.

In addition, model based MNAR methods such as the shared parameter model⁴⁶ and random coefficient pattern mixture model⁴⁴ will be also performed.

